2.2.3 Study Procedures

Participants are inducted onto their assigned XR-NTX induction regimen: SP (Table 3) or RP (Table 4). These regimens are guidelines to be applied by the clinical teams with coaching from the lead team and may be modified by the site clinician based on the clinical status of each patient.

Table 3: Standard Induction Procedure	
Day 1	All participants will receive buprenorphine 6 mg. If participants continue to experience significant withdrawal (COWS > 6) they can receive additional 2-4 mg.
Day 2	Buprenorphine 6 mg in AM
Day 3	Buprenorphine 4 mg in AM
Day 4	Buprenorphine 2 mg in AM
Day 5	Buprenorphine 1 mg in AM
Days 6-13	Adjunctive medications as needed (i.e., clonidine and clonazepam)
Day 13 or 14	XR-NTX eligibility determination followed by the XR-NTX injection

Table 4: Rapid Induction Procedure	
Day 1	All participants will receive buprenorphine 6 mg. If participants continue to experience significant withdrawal (COWS > 6) they can receive additional 2-4 mg. Adjunctive medications will be initiated, if necessary, to alleviate residual withdrawal persisting after administration of buprenorphine 10 mg.
Day 2	Standing doses of clonidine and clonazepam, with additional adjunctive medications as needed*.
Day 3	Standing doses of clonidine and clonazepam, with additional adjunctive medications as needed*. Following the first morning dose of adjunctive medication, participants will receive naltrexone 0.5 mg. If there is no significant increase in withdrawal over the subsequent 120 minutes (COWS increase < 3) they will receive additional naltrexone 0.5 mg.
Day 4	Standing doses of clonidine and clonazepam, with additional adjunctive medications as needed*. Following the first morning dose of adjunctive medication naltrexone 1 mg. If there is no significant increase in withdrawal over the subsequent 120 minutes (COWS increase < 3) they will receive additional naltrexone 1 mg.
Day 5	Standing doses of clonidine and clonazepam, with additional adjunctive medications as needed*. Following the first morning dose of adjunctive medication they will receive naltrexone 3 mg. If there is no significant increase in withdrawal over the subsequent 120 minutes (COWS increase < 3) they will receive additional naltrexone 3 mg.
Day 6	Standing doses of clonidine and clonazepam, with additional adjunctive medications as needed*. Following the first morning dose of adjunctive medication they will receive naltrexone 6 mg. If there is no significant increase in withdrawal over the subsequent 4 hours (COWS increase < 3) participant will receive an injection of XR-NTX 380 mg IM. For those who were not able to tolerate naltrexone 6mg, please refer to Day 7 procedure.
Day 7	Standing doses of clonidine and clonazepam, with additional adjunctive medications as needed*. Participants that were not able to tolerate naltrexone 6 mg during Day 6 will have procedures from Day 6 repeated.

Table 4: Rapid Induction Procedure

*Adjunctive medication to be administered during days 1-7	
clonidine 0.2 mg every 4 hours (lower or withhold the dose if SBP< 90 or HR< 50), MDD=1.2 mg/dclonazepam 1 mg every 6 hours (withhold the dose if the patient is difficult to arouse), MDD=4 mg/dtrazodone 100 mg at night as needed for insomniaprochlorperazine 10 mg every 8 hours as needed for nauseazolpidem 10 mg at night as needed for insomniaibuprofen 600 mg po every 8 hours as needed for muscle pain
--	--

2.2.4 Randomization

Randomization will be performed at the site (cluster) level. Six sites that have the required characteristics to be included in this study will be randomized to the order in which they begin to implement the RP for XR-NTX induction in place of SP. Patient-participants will be treated with the SP or RP according to which procedure is being used at the site at the time the patient is enrolled. The randomization of each site will follow the stepped-wedge design (Table 2). At the selected time points each 14 weeks apart (week 1 = start of enrollment at all 6 sites, weeks 14, 28, 42, and 56), one randomly selected site will make a “step” and will cross-over from the SP to RP. Note that the first randomized site will be in the RP arm for the entire duration of the study whereas the 6th site (after 5 sites have been randomized to the RP) will be in the SP arm for the entire duration of the study. The randomization procedure will be conducted centrally through the NIDA Data and Statistics Center (DSC). The DSC statistician will conduct the randomization at each step and inform the lead node (LN) team and NIDA representatives via email 8 weeks before the study starts (i.e., all sites are ready to start enrollment) or 8 weeks before each transition to the next step.

2.2.5 Blinding

This is a pragmatic unblinded open-label study and thus there is no blinding to the induction procedure being implemented at each site.

2.2.6 Eligibility Criteria for Selection of Study Population

2.3 Participant Inclusion Criteria

Study participants must meet all of the following inclusion criteria in order to be eligible to participate in the study:

1. 18 years of age or older.
2. Meets DSM-5 criteria for current opioid use disorder.
3. Seeking treatment for opioid use disorder, willing to accept treatment with XR-NTX and, in the judgment of the treating physician, is a good candidate for naltrexone-based treatment.
4. Willing and able to provide written informed consent.
5. Able to speak English sufficiently to understand the induction procedures and provide written informed consent to participate in the study.
6. If female of childbearing potential, willing to practice an effective method of birth control for the duration of participation in the study.

2.4 Participant Exclusion Criteria

Participants meeting any of the following exclusion criteria will be excluded from study participation:

1. Serious medical, psychiatric or substance use disorder that, in the opinion of the study physician, would make a detoxification and naltrexone initiation, or maintenance treatment with XR-NTX, hazardous (relative contra-indications) or requires a different level of care. Examples include:
 - a) Disabling or terminal medical illness (e.g., uncompensated heart failure, severe acute hepatitis, cirrhosis or end-stage liver disease) as assessed by medical history and/or review of systems.
 - b) Severe, untreated or inadequately treated mental disorder (e.g., active psychosis, uncontrolled manic-depressive illness) as assessed by history and/or clinical interview.
 - c) Current severe alcohol, benzodiazepine, or other depressant or sedative hypnotic use likely to require a complicated medical detoxification (routine alcohol and sedative detoxifications may be included).
 - d) Suicidal or homicidal ideation that requires immediate attention.
2. Known allergy or sensitivity to buprenorphine, naloxone, naltrexone, polylactide-co-glycolide, carboxymethylcellulose, or other components of the Vivitrol® diluent.
3. Maintenance treatment with methadone within 14 days of consent.
4. Maintenance treatment with buprenorphine unless the patient is determined to have a poor treatment response (in the form of buprenorphine non-adherence with or without the use of illicit opioids), warranting change to XR-NTX treatment.
5. Presence of pain of sufficient severity as to require ongoing pain management with opioids.
6. Circumstances (legal, personal, occupational) that would threaten the feasibility of XR-NTX treatment or make another treatment (e.g., buprenorphine or methadone) a better choice.
7. Are currently in jail, prison or other overnight facility as required by court of law or have pending legal action that could prevent participation in study activities.
8. If female, currently pregnant or breastfeeding, or planning on conception.
9. Body habitus that, in the judgment of the study physician, precludes safe intramuscular injection of XR-NTX (e.g., BMI>40, excess fat tissue over the buttocks, emaciation).
10. Admitted to the inpatient detoxification or residential rehabilitation unit more than 4 calendar days prior to enrollment into to SP or RP.

3.0 GENERAL ANALYSIS POPULATIONS, DEFINITIONS, AND CONVENTIONS

3.1 Analysis Populations

3.1.1 Pre-screened Population

The pre-screened population consists of all patients evaluated for candidacy for XR-NTX and for basic study eligibility criteria as listed on the ENRA form.

3.1.2 Screened Population

The screened population consists of participants who sign the informed consent (IC) at the initiation of the screening process. All screened participants are captured on the ENRB form. Screen failures and reasons for failure are captured on the ENRZ form.

3.1.3 Intent-to-Treat Population

The Intent-to-Treat (ITT) population consists of participants who enroll in the study in either Standard Procedure (Segment C) or Rapid Procedure (Segment D). This will be determined by the induction procedure the site is assigned to at the time of participant enrollment.

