6.0 STUDY DESIGN

6.1 Overview of Study Design

6.1.1 Overview

This is a six-center, stepped-wedge, cluster randomized trial comparing effectiveness and safety of Rapid (5-7-day) versus Standard (13-day) XR-NTX induction procedure (RP vs. SP). Sites will be addiction treatment programs offering inpatient/residential “detoxification” and follow-up outpatient treatment (site characteristics are described in Section 9.0). Patient-participants will be admitted to these sites for treatment of opioid use disorder, eligible for and seeking treatment with XR-NTX, and consenting to research assessments during their course of XR-NTX treatment. Upon enrollment in the study, participants will receive the naltrexone initiation regimen being offered at the site at the time of admission, either SP or RP depending on the random assignment as per study design (Figure 1). The post-induction phase will begin the day after receiving XR-NTX injection. During the 8-week post-induction phase, participants will receive medication management visits per the site’s standard clinical practice, plus an additional two XR-NTX injections, one at four weeks and one at eight weeks after the first XR-NTX injection, along with other psychosocial treatment as per the standard of care provided by each site. The primary effectiveness outcome measure is induction success defined as the administration of the first XR-NTX injection. The primary implementation outcomes derive from the process evaluation of implementation using the CFIR framework and evaluation methods.

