6.1.4 Training in SP and RP procedures

At the beginning of the trial all sites will receive training in the study procedures. In addition, the five sites chosen to offer SP will receive an overview training and review of practices in the SP, while the site selected to start with RP in Step 1 will receive an overview training in the RP. This didactic training will occur before the study start date. At the start date participant enrollment begins, the units chosen to begin by offering SP will receive academic detailing in SP, while the unit assigned to begin RP will receive the further targeted RP implementation facilitation intervention (training and academic detailing) in an 8-week pre-implementation or preparation phase before the start of the RP implementation step. Upon transition to RP implementation (or start of the step), RP academic detailing and coaching support will be held weekly or more frequently based on the site's needs. After individual site-level coaching support sessions, all sites randomized to RP will participate in collaborative coaching sessions that occur weekly or more frequently based on sites' needs.

Study Schema

The flow of a patient-participant through the study, at either SP or RP sites, will proceed in four phases (see Figure 1).

6.1.4.1 *Phase 1 & 2 Inpatient Induction (Recruitment and Induction Phase)*

The clinical procedures for all individuals interested in XR-NTX will be determined by the assignment of the unit to either the Rapid or Standard Procedures and the clinical judgement of the unit staff. These will begin immediately upon admission and will be independent of study participation. Recruitment for research participation will occur independent of the clinical procedures any time from seven days before admission until the fourth day of admission.

Research Recruitment

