10.3 Randomization

Randomization will be performed at the site level. Six sites that have the required characteristics to be included in this study will be randomized to the order in which they begin to implement the RP. Patient-participants will be treated with the SP or RP according to which procedure is being used at the site at the time the patient is admitted.

The randomization of each site will follow the stepped-wedge design (Table 1). At the selected time points as described in the Study Timeline section , one randomly selected site will make a "step" and will cross-over from the standard to the Rapid XR-NTX induction. Note that the first randomized site will be in the Rapid Procedure arm for the entire duration of the study whereas the 6th site (after 5 sites have been randomized to the Rapid Procedure) will be in the Standard Procedure arm for the entire duration of the study and will never switch to the Rapid Procedure.

The DSC statistician will conduct the randomization and inform the sites eight weeks before the selected site is scheduled to transition.

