2.2 Study Design and Procedures

2.2.1 Study Design

This is a six-center, stepped-wedge, cluster randomized trial comparing effectiveness and safety of Rapid (5-7 days) versus Standard (13 days) XR-NTX induction procedure (RP vs. SP). The study will proceed in five steps, with each step lasting 14 weeks, for the total of 70 weeks of the study (Table 2). A total of 450 participants (15 per site per step) eligible for and seeking treatment for opioid disorder with XR-NTX and consenting to research assessments during their course of XR-NTX treatment are planned to be enrolled in the study. Enrolled participants will receive the naltrexone initiation regimen being offered at the site at the time of admission, either SP or RP depending on the random assignment as per study design. At the beginning of each step a randomly selected site will begin implementing RP and will continue to offer it for the remainder of the trial, according to the optimized stepped-wedge study design (Thompson et al., 2017). Note the first randomized site will offer only RP whereas the last remaining site will offer only SP for the entire duration of the trial. After sites transition to RP, this will be the only regimen available for patients interested in participating in the research study (i.e., SP will no longer be offered as a part of the study). Before each stepped wedge of the study, an 8-week pre-implementation or preparation phase will occur for each site randomized to RP. During the implementation phase of RP, the implementation team will meet routinely to review the implementation process and identify modifiable barriers or facilitators to facilitate RP implementation. After each stepped wedge, the study team with expertise in implementation will meet to review identified barriers and facilitators to implementing the RP intervention and modify or adapt the RP Implement Facilitation package accordingly. Site level and provider/staff level surveys will be completed before and after implementation of RP.

Table 2: Schematic of study design with six study sites and five steps, each lasting 14 weeks

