10.0 SAFETY OUTCOMES AND ANALYSIS

Safety outcomes for this study include targeted safety events, serious adverse events, death, injection site abnormalities, overdoses, suicide risk, and pregnancy. Safety outcomes analysis will be performed on the safety analysis population as defined in Section 3.1.4. Safety outcomes will be summarized by induction procedure (SP or RP) and overall. The induction procedure will be determined by the induction procedure the site was assigned to at the time of participant enrollment.

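### The documents fix the arm at two different times, admission and enrolment, so a patient who straddles a site's crossover can be analysed as RP after starting SP

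*SAP*

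**What the plan says.** Three places tie treatment to admission:

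- Protocol 10.3: patients are treated "according to which procedure is being used at the site at the time the patient is admitted".
- Protocol 6.1.1: "participants will receive the naltrexone initiation regimen being offered at the site at the time of admission, either SP or RP".
- SAP 2.2.1: "Enrolled participants will receive the naltrexone initiation regimen being offered at the site at the time of admission".

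Three places in the SAP use enrolment:

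- SAP 2.2.4, on treatment: "according to which procedure is being used at the site at the time the patient is enrolled". The sentence otherwise follows Protocol 10.3 closely.
- SAP 3.1.3, on the intent-to-treat arm: "This will be determined by the induction procedure the site is assigned to at the time of participant enrollment".
- SAP 10.0, on the safety arm: "The induction procedure will be determined by the induction procedure the site was assigned to at the time of participant enrollment".

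The two dates can differ. On clinical procedures, Protocol 6.1.4.1 says: "These will begin immediately upon admission and will be independent of study participation". Exclusion criterion 10 (Protocol 8.2, SAP 2.4) allows up to 4 calendar days between admission and enrolment. SAP 2.2.2 requires eligibility to be settled by Day 4, which is a 3-day lag when admission is Day 1. SAP 8.3 (item 2) reports six participants enrolled later than 4 days under protocol v2.0.

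The primary model in SAP 8.2 adjusts for step 1 to 5 but does not say which date sets a participant's step.

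**The concern.** The SAP contradicts both itself and the protocol on the definition of exposure in the primary analysis and the safety tables. A patient admitted shortly before a crossover and enrolled shortly after it is SP under one set of passages and RP under the other. If such a patient stays on the procedure begun at admission, an SP-treated patient is counted as RP. That pulls the RP–SP contrast toward zero. When RP is truly worse by about the margin, this pull favours a finding of non-inferiority.

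The dates also differ in how exposed they are to influence. The trial is open-label, crossover dates are announced eight weeks ahead (Protocol 10.3), and consent and screening times are flexible (Protocol 10.1). For a patient already admitted, enrolment therefore falls after treatment has begun and at a time staff can affect. Admission is fixed before any response to treatment is seen. Nothing in the documents suggests that enrolment dates were managed in this way; the definition merely allows it.

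No planned analysis isolates these patients. The pre-implementation exclusion (SAP 8.3, item 3) removes SP participants from the 8 weeks before crossover. A straddler enrolled after the crossover carries the RP label and stays in.

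**Working it through.** **Inputs.** Six sites, five 14-week (98-day) periods, 15 participants per site per period, success 0.55 (SP) and 0.70 (RP), margin OR 0.67, site SD 0.86, stated power 0.887 (SAP 12.0). Four sites cross over during enrolment (SAP Figure 1). The test is one-sided at 0.025 (SAP 11.0).

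**1. Reproduce the stated power.** Generalised least squares on the logit scale, with the 6 × 5 design, binomial weights, fixed step effects and a random site effect of SD 0.86, gives SE 0.3361 for the log odds ratio. The planned effect is log 1.909 = 0.6466, and log 0.67 = −0.4005.

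Power = Φ[(0.6466 + 0.4005)/0.3361 − 1.96] = Φ(1.16) = 0.876, against 0.887 stated. This is close enough to use for the size of a change.

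**2. Expected straddlers.** Number = 4 crossovers × (15/98 per day) × lag in days = 0.612 × lag.

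| Lag (days) | Planned rate | Rate from SAP Table 39 |
|---|---|---|
| 1 | 0.6 | 0.6 |
| 3 | 1.8 | 1.7 |
| 4 | 2.4 | 2.3 |

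The last column is a check. The Table 39 footnote gives 32 SP enrolments in the 8 weeks before crossover, so 32/56 = 0.571 per day across the crossing sites.

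**3. Effect if every straddler is treated as SP and analysed as RP.** With k straddlers per crossover, success in each crossing site's first RP period becomes [(15 − k) × p(RP) + k × 0.55]/15. For 1.84 in total, k = 0.46, and 0.70 becomes (14.54 × 0.70 + 0.46 × 0.55)/15 = 0.695. Refitting gives:

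| Straddlers | OR, planned effect | Power | OR, RP at 0.45 | One-sided type I error |
|---|---|---|---|---|
| 0 | 1.909 | 0.876 | 0.669 | 0.0248 |
| 1.84 (3 days) | 1.883 | 0.868 | 0.675 | 0.0263 |
| 2.45 (4 days) | 1.875 | 0.866 | 0.677 | 0.0268 |

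At a 3-day lag, type I error rises by 0.0015 and power falls by 0.8 points. At 4 days the changes are 0.0020 and 1.0 point.

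**4. Simulation check.** The mixed model was fitted to 2,000 simulated trials with normal site effects and the normal quantile 1.96. Power was 0.852 with no straddlers and 0.842 with one per crossover (four in all, over twice the 1.8 above). At the margin the rejection rates were 0.045 and 0.0565. The starting level of 0.045 has nothing to do with straddling, since it arises with none; the run also used a normal quantile, whereas the SAP plans Satterthwaite degrees of freedom. The difference of 0.0115 has a Monte Carlo standard error of √(0.045 × 0.955/2000 + 0.0565 × 0.9435/2000) = 0.0069. The simulation therefore cannot resolve a shift as small as those in step 3. It agrees on direction.

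**The case against.** The strongest reply is that label and treatment may agree. SAP 2.2.4 sets treatment at enrolment too. Protocol 6.1.3 makes RP the only regimen for study patients after transition. Protocol 10.2 says treatment in the first four days follows what the site is then offering. If sites worked that way, the enrolment label matches the procedure the patient went on to receive, and relabelling by admission would create a mismatch. Classifying by the site's assignment at study entry is also a recognisable intent-to-treat convention. The Day 1 buprenorphine guidance is the same in Tables 6A and 6B, so a patient enrolled the day after admission may have received nothing specific to SP.

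Most of this stands. A reader might infer that straddlers were in fact analysed in an arm they did not receive. The documents do not support that, because they do not show which rule sites followed. What remains is that Tables 6A and 6B diverge from Day 2. A patient admitted under SP guidance and enrolled on Day 3 or 4 after a crossover could not have followed the RP schedule from the start on either reading.

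A reader might also count from consent, which can precede admission by 7 days, and reach a larger number. That does not follow. The SAP rule uses enrolment, which comes after eligibility is confirmed (Protocol 10.1.3). The admission date is recorded on the enrolment forms (SAP 3.2.1), and no passage says enrolment can be completed before admission. Such a patient would in any case carry the opposite error, an SP label with RP treatment, so the two groups could not be added as misclassified RP patients.

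**Conclusion.** The conflict is real and sits in the definition of exposure for the primary intent-to-treat analysis, so the SAP should settle it. Its likely effect is small: about 0.6 to 1.8 of 450 participants at lags of 1 to 3 days, 2.4 at 4 days, with type I error moving from 0.025 to about 0.026 and power by about 1 point.

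These figures assume uniform enrolment, the full lag for every participant and all straddlers misclassified, so for a given lag they are upper bounds on the expected effect. The six participants enrolled beyond 4 days fall outside the range. The pull toward non-inferiority applies near the margin; at the planned effect the same dilution works against declaring it. The choice of date also affects step labels near step boundaries at every site. That effect depends on the secular trend and was not quantified.

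**What to change.** - **One date.** Reconcile SAP 2.2.1, 2.2.4, 3.1.3 and 10.0 so that a single date sets both analysis arm and step for enrolled participants, and name it where SAP 8.2 defines step. Admission (E97ADMDT, on the ENRC and ENRD forms) matches Protocol 6.1.1 and 10.3 and precedes any response to treatment.
- **Safety.** State separately how consented patients who never enrol are classified. The safety population is everyone who signs consent (SAP 3.1.4), but these patients have no ENRC or ENRD record and no enrolment date, so neither date classifies them.
- **Straddlers.** Report how many participants were admitted before and enrolled after a crossover. If there are any, repeat the primary analysis with the alternative date.
- **Treatment.** Which procedure governs the care of a straddling patient is for the sponsor to reconcile across Protocol 6.1.1, 6.1.3, 10.2 and 10.3 and SAP 2.2.1 and 2.2.4.

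The cost is a few sentences in the SAP, one count and at most one repeated model. Both dates are already recorded for enrolled participants, so no new data are needed.
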